# 2.2 Rationale for the use of stereotactic body radiation therapy in pancreatic cancer

Recent advances in radiation treatment technology, including improvements in planning systems, patient immobilization equipment, image-guided radiation therapy technologies, and radiation delivery mechanisms, have permitted the development of stereotactic body radiation therapy (SBRT), which permits the intensification of therapy by delivering increased daily doses of radiation to highly focused targets within the body. Several phase II trials of SBRT in patients with pancreatic cancers have been performed, showing that the technique is well tolerated and is associated with improvements in local control rates compared with historical series of conventionally fractionated chemoradiation. Koong et al. used the Cyberknife™ stereotactic radiosurgery system to demonstrate that a single 25-Gy dose stereotactic body radiotherapy (SBRT) was feasible for patients with locally advanced pancreatic cancer. (17) Furthermore, this dose of radiation resulted in near 100% progression free survival and effectively palliated symptoms related to the local growth of pancreatic tumors. Based on this study, the same group also completed a phase II study assessing the efficacy of combining a standard fiveweek course of chemoradiotherapy followed by a stereotactic radiosurgery boost to the primary tumor in patients with locally advanced pancreatic cancer. In this cohort of 19 patients, 100% of tumors were without local progression. However, all patients eventually developed metastases, with a median time to progression of 5.5 weeks. A more recent phase II study treated locally advanced pancreatic cancer patients with induction gemcitabine followed by single-fraction SBRT (25 Gy) and maintenance gemcitabine chemotherapy. In this study, the excellent progression free survival was confirmed from previous studies (81%). The median overall survival was 11.4 months, median time to progression was 9.7 months and the 1 year survival was 50%.(18) There were no significant acute GI toxicities; however, of the 15 patients alive >6 months after Linac

(linear-accelerator)-based SBRT, 7 (47%) experienced Grade 2 or greater GI toxicity, with 2 (13%) of the 15 experiencing Grade 3 or greater GI toxicity.

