To decrease the risk of late GI toxicity, subsequent studies have therefore reduced the per-day dose and prolonged the treatment schedule. For example, Hong et al. reported a neoadjuvant regimen delivering 5 Gy x 5 to the pancreatic tumor plus adjacent lymph nodes using proton beam radiation. (19) This regimen was shown to be safe, with no instances of dose limiting toxicity observed and only 4 of 15 patients developing grade 3 toxicity (no patients experienced grade 4 toxicity). Herman et al. recently published the largest phase II study to date of definitive 5-fraction SBRT in pancreas cancer, which reported a median overall survival rate of 13.8 months. (20) The regimen was also well tolerated, with acute and late grade 2 or greater toxicity rates of 2 and 11%, respectively. SBRT was associated with stable quality of life scores and improving pain scores. Similarly, a grade 3 or greater toxicity rate of 7% was reported in an institutional series of 159 patients treated using five-fraction regimens for both borderline resectable and unresectable tumors. (21)

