# 2.3 Rationale for Selection of Patient Population

As noted previously, local control rates remain unsatisfactory in patients with unresectable pancreatic cancer, up to 30% of whom die with uncontrolled local disease. Local progression of pancreatic cancer can cause distressing symptoms including pain, biliary and gastrointestinal tract obstruction, and pancreatic insufficiency. Furthermore, preliminary data suggest that some patients treated with stereotactic body radiation therapy for unresectable disease achieve sufficient tumor response to proceed to surgical resection; (20) in patients with borderline resectable disease, neoadjuvant SBRT has also been associated with high rates of margin-negative resection. (21)

The development of recurrent pancreatic cancer after definitive treatment with surgery, radiation, chemotherapy, or a combination of these universally portends a dismal prognosis, with the 5-year survival for such patients being 5.6% or less. (24) Unfortunately, this scenario is not uncommon; even among the small number of patients (10-15%) able to undergo potentially curative surgical resection, more than 80% subsequently develop recurrent disease.(25) Following resection, 71-77% develop distant metastases within 2 years, often accompanied by concurrent locoregional recurrence, while up to 30% exhibit isolated locoregional recurrence. (26-29) Patients who develop combined distant/locoregional recurrence have a median survival of 3 months from the time of recurrence, while those with isolated locoregional recurrence have a median survival of 7 months. (28) Locoregional recurrence is, therefore, a common and serious problem both in the setting of metastatic disease and as an isolated entity. Symptomatic manifestations include pain, gastric outlet/small bowel obstruction, portal hypertension, biliary obstruction, and malnutrition. Although survival is determined chiefly by systemic disease control, local control greatly affects quality of life in pancreatic and periampullary cancer patients. (29, 30) Among the majority of patients with pancreatic cancer who present with unresectable disease, chemoradiation is able to transiently stabilize the disease in some patients and to prolong median survival to 8-14 months. (8, 9, 31) Regardless of whether a tumor is resectable or unresectable at diagnosis, the symptoms associated with local recurrence or persistence of disease require swift and effective treatment.

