# 3.2 Secondary Objectives

- To estimate rates of late (> 3 months after treatment) grade 2 gastritis, enteritis, fistula, and ulcer, or any other grade 3 or greater gastrointestinal toxicity in patients treated with Linac-based SBRT for pancreatic or periampullary cancers
- To estimate rates of local progression, overall survival, metastasis-free survival, and progression-free survival in patients with pancreatic or periampullary cancers treated with fractionated Linac-based SBRT.
- To evaluate the ability of Linac-based SBRT to provide pain control in patients with pain related to a pancreatic or periampullary tumor.
- To evaluate quality of life in patients undergoing treatment with Linac-based SBRT for pancreatic or periampullary cancers.

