#### 10. CRITERIA FOR EVALUATION/REMOVAL FROM STUDY

# **10.1** Anti-Tumor Effect and Response Evaluations

Patients will be evaluated for anti-tumor effect by follow-up imaging (pancreas protocol CT and/or PET-CT imaging) as outlined above. All subsequent scans (post-treatment) will be compared to the same pretreatment CT or PET/CT that was performed for radiation treatment planning. Evaluation of pancreatic and periampullary tumor response will be based on standard radiographic criteria for the treated lesion and will be prospectively recorded in the study database. Radiographic response of the pancreatic or periampullary tumor by diagnostic CT scans will be defined according to RECIST criteria as described below:

- CR = complete disappearance of index lesion
- PR = at least 30% decrease in the longest diameter of the index lesion PD = more than 20% increase in the longest diameter of the index lesion SD = does not meet criteria for PR or PD
- Local tumor progression will be defined as >=20% increased size on CT scan compared to a CT scan from prior to treatment.
- Distant progression will be defined as any new tumor found outside of the pancreas or periampullary region on CT scan.

Pancreatic or periampullary tumor response will also be assessed by FDG-PET scans (when available) according to the following criteria:

- CR = target lesion becomes photopenic or standardized uptake value (SUV) ratio of tumor/liver less than or equal to 1
- PR = decrease in SUV ratio of tumor/liver (at least 30%) PD = increase in SUV ratio of tumor/liver (at least 20%)
- SD = no significant change in SUV ratio of tumor/liver

We will also determine PET response (in those patients who have undergone follow-up FDG PET scanning) with the new PERCIST criteria as reported by Wahl et al., defined as follows: (33)

- Complete metabolic response (CMR): complete resolution of 18F-FDG uptake within the measurable target lesions so that it is less than mean liver activity and indistinguishable from surrounding background blood-pool levels with no new 18F-FDG avid lesions
- Partial metabolic response (PMR): reduction by a minimum of 30% in the target lesion's 18F-FDG peak
- Stable metabolic disease (SMD): disease other than CMR, PMR, or progressive metabolic disease
- Progressive metabolic disease (PMD): 30% or greater increase in 18F-FDG peak in the target lesion or the development of new 18F-FDG avid lesions that are typical of cancer.

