#### 10.2 Definitions

- Duration of Response: time elapsed between SBRT completion (i.e., the last day
  of treatment) and the first sign of local progression or the development of new
  metastatic disease.
- Progression-Free Survival: time elapsed from SBRT completion to documented local/regional or distant progression or death. Local PFS will be measured as the duration from SBRT to local progression or death from any cause.
- Overall Survival: Duration from SBRT completion to patient death.

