# 11.10 Analysis of Secondary Objectives

Acute toxicities according to CTCAE 4.0 will be summarized by frequencies and rates calculated as the proportion of patients in the safety population experiencing SAEs, discontinuations due to AEs, and AEs for the two cohorts combined. For the secondary objective of estimating rates of late (> 3 months after treatment) grade 2 gastritis, enteritis, fistula, and ulcer, or any other grade 3 or greater gastrointestinal toxicity, the proportion of patients with each condition and its 90% confidence interval will be calculated.

In Cohort B only, Kaplan-Meier estimates will be used to estimate the median and 90% confidence intervals for time to local progression, overall survival, metastasis-free survival and progression-free survival. The 1-year rates and 90% confidence intervals will be also be estimated from these curves. A listing of clinical outcomes will be generated for Cohort A.

Pain control (based on reporting of standard pain score (0-10) with the option to use the FACES 0-10 scale) will be evaluated before and after Linac-based SBRT and the change in pain scores will be evaluated and summarized through descriptive statistics separately for each cohort. For Cohort B, linear mixed models will be used to model changes in pain over time. A similar approach will be used for the EORTC QOL-Q scale.

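### Kaplan-Meier for time to local progression does not yield the local progression rate sought in objective 3.2, whether deaths are censored or counted as events

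*Combined protocol and SAP*

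**What the plan says.** Objective 3.2 of the combined protocol and SAP includes: "To estimate rates of local progression, overall survival, metastasis-free survival, and progression-free survival". Section 11.10 gives the method, for Cohort B only: "Kaplan-Meier estimates will be used to estimate the median and 90% confidence intervals for time to local progression", with the three survival endpoints handled alike. It adds: "The 1-year rates and 90% confidence intervals will be also be estimated from these curves".

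The event is defined in section 10.1: "Local tumor progression will be defined as >=20% increased size on CT scan", relative to a pre-treatment scan. Death is not part of it. Section 10.2 defines progression-free and overall survival, and a further composite: "Local PFS will be measured as the duration from SBRT to local progression or death from any cause". It does not define time to local progression, and section 11.10 does not list local PFS. Competing risks and cumulative incidence are mentioned nowhere.

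**The concern.** Death without local progression is a competing event: once it happens, local progression can no longer be observed. A Kaplan-Meier curve can treat it in only two ways.

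- **Censored.** This is the usual default when death is not in the event definition. The curve then treats patients who have died as if they could still progress at the same rate as those still followed, and 1-KM exceeds the proportion who actually progress.
- **Counted as an event.** The result is local PFS under another name, which mixes deaths from systemic disease with local failures.

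At stake is whether the figure reported for local progression means what objective 3.2 says. The gap grows with the number of deaths that occur first, and the background leads one to expect many.

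**Working it through.** The plan states no expected value or precision for local progression, so there is no figure of its own to reproduce. The check is how far 1-KM lies from the cumulative incidence under the background figures.

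**Inputs**

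- Survival: section 2.2 cites a five-fraction study "which reported a median overall survival rate of 13.8 months" and a single-fraction study: "The median overall survival was 11.4 months, median time to progression was 9.7 months and the 1 year survival was 50" per cent. Section 2.3 says of recurrence after resection that "those with isolated locoregional recurrence have a median survival of 7 months". With exponential survival, the 1-year survival is 0.5^(12/median): 54.7% (13.8 months), 48.2% (11.4 months) and 30.5% (7 months).
- Share of deaths without local progression: section 2.1 attributes about 30% of deaths to local progression. The remaining 70% serves as a proxy, varied from 50% to 90%.
- 1-year local failure by Kaplan-Meier: 38% (62% local control in the re-irradiation series, section 2.3), 19% (the 81% figure in section 2.2, assumed to be a 1-year local figure) and 50% (section 2.1 gives local control below 50% with conventional chemoradiation).
- Cohort B size: about 30 (section 11.5).

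**Formulas** (constant hazards, time in years)

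- L = -ln(1 - local failure by Kaplan-Meier)
- D = 12 × ln2/median × share
- 1-KM at 1 year = 1 - exp(-L)
- Cumulative incidence = L/(L+D) × [1 - exp(-(L+D))]
- Local PFS event rate = 1 - exp(-(L+D))

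**Worked case: 13.8 months, 70% share, 38% local failure**

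- L = -ln(0.62) = 0.478
- D = 12 × 0.693/13.8 × 0.7 = 0.422
- Cumulative incidence = 0.478/0.900 × (1 - exp(-0.900)) = 31.5%, against 38% by 1-KM: 6.5 points too high
- Deaths first, without local progression: 0.422/0.900 × 0.593 = 27.8%, about 8 of 30 patients
- Local PFS event rate: 59.3%, so counting deaths as events moves the figure further from 31.5%

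**All cases at a 70% share** (cumulative incidence, with the overstatement by 1-KM in points)

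| Median survival | 1-KM 19% | 1-KM 38% | 1-KM 50% |
|---|---|---|---|
| 13.8 months | 15.6% (3.4) | 31.5% (6.5) | 41.8% (8.2) |
| 11.4 months | 15.0% (4.0) | 30.4% (7.6) | 40.3% (9.7) |
| 7 months | 13.1% (5.9) | 26.6% (11.4) | 35.6% (14.4) |

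Varying the share from 50% to 90% over all three medians gives a range from 2.5 points (13.8 months, 50%, 19%) to 17.4 points (7 months, 90%, 50%).

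**Simulation of the worked case** (n = 30, 20,000 replicates, no other censoring): mean 1-KM is 38.1% (SD about 10 points) and mean cumulative incidence is 31.6% (SD about 8 points).

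**The case against.** The strongest reply is that the plan never says deaths are censored, so what it demonstrably lacks is a definition. That is so, and a reader should not infer that the reported rate is bound to be overstated by censoring. But the omission does not rescue the plan, because the other Kaplan-Meier reading gives local PFS.

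It can also be said that objective 3.2 does not specify a crude proportion, and that 1-KM estimates a net rate as if nobody died. The documents do not claim that quantity. It would require patients who die to have the same underlying local risk as those who survive, which the data cannot verify.

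On size, a reader might apply the full all-cause death hazard to the 38% case. That gives cumulative incidences of 23%, 28% and 29% at 7, 11.4 and 13.8 months, an overstatement of about 9 to 15 points. This leans high: some deaths follow local progression and do not compete with it. The 7-month median describes isolated recurrence after resection, whereas Cohort B also takes unresectable and borderline resectable disease. The 62% comes from 18 re-irradiated patients, which is the Cohort A setting.

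A reader might also infer that the trial's rate could not fairly be compared with the local control figures in the background. The documents do not say how those figures were estimated, and the plan specifies no such comparison. If they are Kaplan-Meier figures, 1-KM would be the like-for-like one.

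Finally, the stakes are modest. The primary outcome is acute toxicity, section 11.5 puts the focus on safety, and the 1-year outcome measures in section 3.3.2 omit local progression. Nothing supports calling local control the main efficacy question. With about 30 patients the sampling SD is at least as large as the central bias. All of this stands, but it limits the weight of the point without removing it: the bias under censoring is systematic, always upward and avoidable.

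**Conclusion.** The point holds. As written, section 11.10 does not deliver the local progression rate of objective 3.2 under either handling of death. If deaths are censored, the direction is certain as soon as any death without local progression precedes a later local progression. The size is not fixed by the documents: about 3 to 10 points with medians of 11.4 to 13.8 months and a 70% share, and about 2.5 to 17 points over the wider range. These figures rest on constant hazards, the 70% proxy and local failure rates from other populations, and should be read as an illustration. The consequence is confined to one secondary endpoint of a pilot study. The primary outcome, stopping rule and sample size do not depend on it. The change is worth making because a better-matched estimator is available at almost no cost.

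**What to change.** - **Section 10.2:** define time to local progression as running from SBRT completion to local progression as in section 10.1, with death without local progression as a competing event.
- **Section 11.10:** for this endpoint, replace 1-KM and the Kaplan-Meier median by the Aalen-Johansen cumulative incidence, with the 1-year rate and its 90% confidence interval.
- If a composite is wanted, report local PFS by Kaplan-Meier under its own name.
- Keep Kaplan-Meier for overall, progression-free and metastasis-free survival. The last is not defined in section 10.2, and its definition should state that death is an event.

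The cost is a sentence or two in each section. Dates of progression and death are already needed for the survival endpoints, so no new data are required. One small downside is that the result may be less directly comparable with any published Kaplan-Meier local control rates. Showing the Kaplan-Meier figure as a labelled supplementary result, with its handling of death stated, meets this.

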#### 3.3.2 Secondary Outcome Measures

• Late (> 3 months after treatment) toxicity rates (as raw percentage), as related to the RTOG Late Radiation Toxicity Grading Scale.

- One-year rates of overall, progression-free, and metastasis-free survival (will
  continue to obtain data on these outcomes at subsequent visits beyond 1
  year, but the 1 year time point will represent the outcome measure of
  interest)
- Pain control at one and three months after treatment (based on reporting of standard pain score (0-10) with an option to record pain score based on FACES assessment scale) –will continue to obtain data on pain control at subsequent visits but these 2 time points will represent the main outcome measures of interest
- Quality of life at each follow-up visit (measured by EORTC QOL-Q scale) will
  continue to obtain data on quality of life at subsequent visits but these 2 time
  points will represent the main outcome measures of interest

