#### 7.4.2 Other Concomitant Medications

Therapies considered necessary for the patient's well-being may be given at the discretion of the investigator. Other concomitant medications should be avoided except for analgesics, chronic treatments for concomitant medical conditions, or agents required for life-threatening medical problems. Specifically, if the patient is being treated with chemotherapy, it is recommended that chemotherapy be discontinued at least one week prior to initiation of Linac-based SBRT and that resumption of chemotherapy be delayed for at least one week following the conclusion of Linac-based SBRT. In general, prescription of these medications will be presided over by the patient's attending medical oncologist.

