Patients' responses to therapy will also be evaluated clinically after completion of their Linac-based SBRT. The following are clinical definitions for response:

• CR = complete alleviation of pain or other symptoms thought to be related

- to the index lesion
- PR = improvement, but not complete elimination, of pain or other symptoms thought to be related to the index lesion
- PD = worsening of pain or other symptoms thought to be related to the index lesion
- SD = does not meet criteria for PR or PD

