#### 12. DATA FORMS AND SUBMISSION SCHEDULE

This study will utilize electronic Case Report Form completion in the OnCore® database. A calendar of events and required forms are available in OnCore®. The OnCore® database is a comprehensive, web-based, Clinical Trial Management System (CTMS) which utilizes an Oracle database. OnCore® was developed by Forte Research Systems, Inc. and is used by the IUSCC Clinical Trials Office (CTO) and supported by the Indiana Clinical and Translational Sciences Institute (CTSI).

OnCore® provides users secure access with unique IDs/passwords and restricts access by assigned roles, from any location, to record, manage, and report on data associated with the operation and conduct of clinical trials.

All source documents are to remain in the patient's clinic file. All documents should be kept according to applicable federal guidelines. Clinical trial data in OnCore® are periodically monitored by the IU Simon Cancer Center Data Safety Monitoring Committee.

Participant data that will be collected include the following:

- Eligibility or inclusion/exclusion criteria
- Patient demographics
- Pre-study evaluation

- Surgical procedures, with dates and findings (including EUS, biopsy (if needed), fiducial placement, and/or stent placement (if recommended)
- Scan dates (PET/CT (if available) and/or CT)
- Treatment planning date
- Pre-Study labs including hematology, chemistry, and tumor markers (CBC, CMP, and CA 19-9)
- Radiation therapy dates and toxicities reported
- Follow-up evaluations including H&P data, laboratory studies, imaging, and toxicity data
- QOL and pain questionnaires
- Subject study withdrawal, date, and reason
- Participant report of compliance with protocol prescribed medications, specifically PPIs and antiemetics

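### Pain control is read from score change alone with no account of analgesic use, so a change in score cannot be attributed to SBRT

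*Combined protocol and SAP*

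**What the plan says.** **Objective.** Section 3.2 sets out "To evaluate the ability of Linac-based SBRT to provide pain control in patients with pain related to a pancreatic or periampullary tumor". The wording attributes the effect to SBRT.

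**Outcome.** Section 3.3.2 names "Pain control at one and three months after treatment", taken from a 0-10 score with FACES as an option. No analgesic component is mentioned.

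**Analysis.** Section 11.10 states that "the change in pain scores will be evaluated and summarized through descriptive statistics separately for each cohort". It continues: "For Cohort B, linear mixed models will be used to model changes in pain over time". No analgesic covariate is given, and no rule for an increase or reduction in analgesia.

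**Clinical response.** Section 10.1 defines categories on symptoms, beginning "CR = complete alleviation of pain or other symptoms thought to be related" to the index lesion. PR is partial improvement, PD is worsening and SD is the remainder. None carries a condition on analgesics.

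**Permitted medication.** Section 7.4.2 says "Other concomitant medications should be avoided except for analgesics" and a few other classes. It sets no stability requirement, which is ordinary good care.

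**Data.** Section 12 lists the pain and quality-of-life questionnaires. Its only line that names medications is "Participant report of compliance with protocol prescribed medications, specifically PPIs and antiemetics". The Section 9 calendar has a questionnaire row but no row for analgesics or concomitant medication. Section 11.7 plans a table of drugs that could influence the study treatment, without naming analgesics or linking the table to pain.

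**Design.** Section 5 describes one unblinded arm at one center.

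**The concern.** A pain score is taken under whatever analgesia the patient is using that day. If analgesia changes between baseline and the one- or three-month visit, the score can move for a reason unrelated to radiation. There is no comparator arm in which the same drug changes would occur and cancel out.

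The protocol gives pain real weight. Sections 2.1 and 2.3 present it as a main symptom of local disease, and Section 2.3 cites pain relief in 57% of symptomatic patients in a re-irradiation series as support for treatment. A pain result from this study is therefore likely to be read as evidence about SBRT. Under the stated rules, that reading would rest on a quantity that also contains changes in analgesia.

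**Working it through.** The documents give no figure for pain: no expected change, standard deviation, response threshold or sample-size basis. There is nothing to reproduce, so the check is whether the stated rules can separate the two effects.

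**Step 1: what the score change contains.** For one patient, write

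change in score = S + A + N,

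where S is the SBRT effect, A is the effect of any change in analgesia, and N is everything else (disease course, later chemotherapy, natural variation). Sections 3.3.2 and 11.10 use only the left-hand side. Nothing planned for the pain analysis informs A, and with one arm nothing else removes it. The Cohort B mixed model has the same limit: it describes the path of the score over time but has no stated analgesic term.

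**Step 2: the direction of error.**
- Opioids increased, score falls from 7 to 2, with S = 0 and N = 0. Then A = 2 − 7 = −5. Section 11.10 records a 5-point improvement, and the same easing of pain would be a PR in Section 10.1.
- Opioids stopped, score unchanged, with S = −k, A = +k and N = 0. The change is −k + k = 0. Section 11.10 records no change, and Section 10.1 would give SD, although the patient has benefited.

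The errors run in opposite directions, so the sign of the net bias is not known in advance.

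**Step 3: can a size be given?** Only on assumptions that come from outside the documents. Suppose SBRT has no effect, the pre-escalation score stays at its baseline level, 20% to 50% of patients have analgesia increased, and each gains 1 to 3 points of relief. The apparent mean fall is share × relief:
- low end: 0.20 × 1 = 0.2 points
- high end: 0.50 × 3 = 1.5 points

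For comparison, take about 30 Cohort B patients (Section 11.5) and an assumed standard deviation of change of 2 to 3 points. The 90% half-width of the mean change is 1.645 × SD / √30:
- SD 2: 1.645 × 2 / 5.477 = 0.60 points
- SD 3: 1.645 × 3 / 5.477 = 0.90 points

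The upper part of the first range could look like a real improvement. The result depends heavily on the constant-pain assumption. If analgesia is increased because pain has risen by u points, and relief is r points, the net change in those patients is u − r. This is zero when u = r and still a worsening when u > r. The figures show that the effect need not be negligible; they do not estimate it.

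**Step 4: could other planned data fill the gap?** The Section 12 list is introductory rather than exhaustive, it includes follow-up history and physical data, and Section 11.7 implies some medication capture. Analgesic information may therefore exist in charts or forms. No section names it, asks for dose or timing, or ties it to the pain score.

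**The case against.** Several points on the other side are sound.

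- **Not listed is not the same as not collected.** Section 12 refers to forms held in the trial database that are not reproduced, and its PPI and antiemetic line concerns compliance with prescribed drugs rather than concomitant medication in general. A reader might infer that no analgesic data are collected. The documents do not support that. They show only that analgesics are not named and not used in the pain analysis.
- **The responder examples do not belong to the planned pain analysis.** The categories are in Section 10.1; they are not among the Section 3.3.2 outcomes and are not analysed in Section 11.10. No pain response rate is stated anywhere, so it would be wrong to say that the plan's response rate is inflated.
- **The bias is not one-directional.** A reader might infer that stronger analgesia simply inflates the benefit of SBRT. Step 2 shows that a real benefit can equally be missed.
- **Pain is secondary and the study is a pilot.** No test, threshold or decision depends on the pain result, and Section 11.1 allows additional exploratory analysis.
- **Analgesic data would not give full attribution.** Section 7.3 leaves later chemotherapy to the treating oncologist, and there is no control arm.

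These points limit the strength of the claim and keep it a modest one. They do not remove it: permission to explore is of little use if analgesic use was not recorded in usable form at each score, and residual confounding is no reason to leave an easily recorded source unmeasured.

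**Conclusion.** The concern holds in a limited form. The pain outcome and the symptom-based response categories take no account of analgesic use, which is freely permitted and not named for collection. Score change therefore mixes SBRT effect with analgesic change, and an observed change cannot be attributed to SBRT.

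The bias can go either way and its size cannot be derived from the documents; the ranges in the working rest entirely on assumed inputs. It would be too strong to say that the pain objective cannot be addressed at all, because the course of the scores can still be described. The primary toxicity estimate is untouched. This is a cheap improvement to a secondary outcome.

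**What to change.** **Section 12 and the Section 9 calendar.** Add current analgesic use at baseline and at each pain assessment, for example daily oral morphine equivalent and any nerve block since the last visit. If this is too much for every visit, cover at least baseline and the one- and three-month time points.

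**Section 11.10.** Keep the raw score change. Report the change in analgesic use beside it, and add a supportive summary with two counts: patients with a lower score and no analgesic increase, and patients with a stable score and reduced analgesics.

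**Section 10.1.** When the pain-based CR and PR categories are reported, apply the same condition of no analgesic increase.

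**Interpretation.** State that confounding by later chemotherapy and the absence of a control arm remain.

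These changes concern recording and reporting only and restrict no patient's analgesia. The cost is modest extra abstraction. It is more than reading off an existing field, because the documents mention a medical history but not a medication history, visits after 4-6 weeks may take place at outside hospitals, and questionnaires may come back by mail. For patients already treated, chart review may recover part of the data. The pain result may also look less favorable.
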